1. INTRODUCTION

Artemisinin combination therapies (ACTs) have been a major driving force behind substantial reductions in global malaria morbidity and mortality over recent years. However, further gains are threatened by the recent emergence of artemisinin resistance in Southeast Asia (1), a region that has been the epicentre for the evolution and spread of resistance to every important class of antimalarials.

ACT is the simultaneous use of two or more blood schizontocidal drugs with independent modes of action. The rationale behind ACT is that the chance of parasites simultaneously developing resistance to two drugs with different modes of action is much lower than the chance of parasites developing resistance to single drugs. Rapid clearance of parasitemia and resolution of symptoms is dependent on artemisinin while the complete clearance of the remaining parasites is dependent on the partner medicine (2). With the emergence of artemisinin resistance, partner drugs have been left exposed to a much larger biomass of parasites and unsurprisingly partner drug resistance has followed (3).

Treatment failures after artemisinin combination therapies are becoming more widespread in Southeast Asia. Failures rates of around 30% for dihydroartemisinin-piperaquine and mefloquine-artesunate have been documented in western Cambodia (4) and western Thailand border areas (5) respectively. Failure of first line ACTs will damage current control and elimination efforts and accelerate the emergence and spread of resistance. A major concern is that artemisinin and partner drug resistance may spread across a wider geographic area, as chloroquine resistance did in the 1960s and 1970s, moving from Southeast Asia to the Indian subcontinent and Africa. Furthermore, while the resistance phenotype is currently limited to the ring stage of the asexual cycle, there is a chance that the resistance itself could 'deepen' by extending beyond this stage, causing more problems in the management of malaria .

There is an urgent need to evaluate alternative treatments where standard courses of ACTs are failing, and to develop combinations of drugs which will not fall rapidly to resistance and can be deployed immediately. As new drugs are at least five years away, we propose to combine artemisinin derivatives with two existing slowly-eliminated partner drugs; triple artemisinin combination therapy (TACT).

The principle that multiple drugs with independent mechanisms of action prevent the emergence of drug resistance is proven in a range of human diseases. In HIV and tuberculosis for example, the occurrence and spread of drug resistance can be prevented by use of a combination of three or more antiretroviral or antimycobacterial therapies respectively, but until now this was not thought necessary in malaria. Interestingly, there is a fortuitous inverse correlation between susceptibility to two important antimalarials, amodiaquine and lumefantrine, which will be exploited in the TACTs.

Choosing partner drug combinations

In general the 'malaria world' can be divided into different areas, based on current resistance patterns and current antimalarial drug use.

The decision on which two partner drugs to combine in any new regimen must take into account pharmacokinetic and pharmacodynamic interactions, locally existing resistance profiles to artemisinin derivatives and the individual potential partner drugs, and the current antimalarial treatment policy.

The global spread of chloroquine (CQ) resistance was also associated with cross-resistance to amodiaquine. However amodiaquine continued to be used in some areas of Southeast Asia, such as Myanmar, owing to its low cost. Relatively few trials of the ACT artesunate-

amodiaquine have been conducted. The largest showed borderline efficacy in Myanmar with recrudescence rates of about 10%. Studies in Vietnam, as well as India and Africa, have reported cure rates above 95% (6-10).

Transfection data provide the most reliable means of understanding the molecular basis of amodiaquine resistance. Fidock and colleagues introduced two major patterns of mutations (Dd2 and 7G8) into wild-type *pfcrt*-encoding parasites and were able to confirm that these mutations were causative factors in CQ resistance (11). Notably there was a clear inverse correlation between the IC50 values for CQ and mefloquine (MQ) as well as for amodiaquine and MQ. In other words, resistance to chloroquine/amodiaquine caused by specific *pfcrt*-mutations was associated with mefloquine hypersensitivity.

A second locus, pfmdrl, also appears to be involved in amodiaquine resistance, with the N86Y mutation associated with resistance in vitro and increased clinical failures with amodiaquine monotherapy (12-14). A recent paper by Venkatesan et al. suggests that recurrent infection after artemether-lumefantrine and artesunate-amodiaquine is associated with specific mutations in the pfmdrl gene, but that the two partner drugs select alternative and drug resistance opposing alleles (15).

In theory, the concurrent use of lumefantrine combined with amodiaquine exploits these opposing selection pressure effects. Potentially, this will prevent or delay emergence of high-level resistance to both drugs at the same time. This would be expected to prolong or maintain the overall efficacy of both partner drug components (16).

To assess the safety and tolerability and pharmacological interactions of the combination of artemether-lumefantrine and amodiaquine we propose an open label sequential trial of artemether-lumefantrine combined with amodiaquine.

As we propose to combine artemether-lumefantrine, and amodiaquine, it is necessary that the potential interactions of these drugs be characterized. These drugs are metabolized by cytochrome P450 (abbreviated CYP) enzymes which potentially causes pharmacokinetic alteration, resulting in clinically significant drug-drug interactions that can cause unanticipated adverse reactions or therapeutic failures because of the suboptimal exposure of the parasite.

Artemether-lumefantrine data

Following administration of artemether-lumefantrine to both healthy volunteers and patients with malaria, artemether is absorbed with peak plasma concentrations reached about 2 hours after dosing. Absorption of lumefantrine, a highly lipophilic compound, starts after a lag-time of up to 2 hours, with peak plasma concentrations about 6 to 8 hours after administration. Food enhances the absorption of both artemether and lumefantrine. In healthy volunteers, the relative bioavailability of artemether was increased between 2- to 3-fold, and that of lumefantrine 16-fold when artemether-lumefantrine tablets were taken after a high-fat meal compared to under fasted conditions. Artemether and lumefantrine are both highly bound to human serum proteins in vitro (95.4% and 99.7%, respectively). In human liver microsomes and recombinant CYP450 enzymes, the metabolism of artemether was catalyzed predominantly by CYP3A4/5. Artemether is cleared from plasma with an elimination half-life of about 2 hours. Lumefantrine is eliminated more slowly, with an elimination half-life of 3 to 6 days in healthy volunteers and in patients with falciparum malaria. Demographic characteristics such as sex and weight appear to have no clinically relevant effects on the pharmacokinetics of artemether and lumefantrine (17).

Amodiaquine data

Amodiaguine by oral administration is absorbed rapidly, and then extensively metabolized to N-desethylamodiaquine (active metabolite) and 2-hydroxy-desethyl-amodiaquine by hepatic first-pass effect. C_{max} of amodiaguine in plasma, whole blood and packed cells is 32±3ng/ml, 60±10ng/ml and 42±6ng/ml respectively; Tmax of amodiaguine is 0.5±0.03h, 0.5±0.1h and $0.5\pm0.1h$ respectively; AUC₀₋₈ of amodiaguine in plasma, whole blood and packed cells is 99 ± 19 ng·ml⁻¹h, 148 ± 25 mJ⁻¹h and 167 ± 72 ng·ml⁻¹h respectively. Cmax of desethylamodiaguine in plasma, whole blood and packed cells is 181±26ng/ml (19 fold higher than those of the parent drug), 561±70ng/ml and 561±143ng/ml respectively; Tmax for desethylamodiaguine is 3.4±0.8h, 2.2±0.5h and 3.6±1.1h respectively; and AUC0-24 for desethylamodiaquine in plasma, whole blood and packed cells is 2304±37ng·ml⁻¹h, 6811±752ng·ml⁻¹h and 5713±1269ng·ml⁻¹h respectively (whole blood AUC was higher than plasma AUC, P<0.001). The trial of ¹⁴C-labelled amodiaquine administered orally to Wistar rats showed that amodiaquine can be distributed widely in body with the main organs of accumulation being kidney, liver, bone marrow and spleen. Amodiaquine is not observed in plasma 8 hours after administration, whereas the concentration of desethylamodiaquine in plasma at 96h is 29 ± 8 ml⁻¹. The half-life of amodiaguine in plasma is 5.2 ± 1.7 h, and elimination half-life ($\beta_{t1/2}$) of desethylamodiaquine in plasma is 9-31 days. The bioavailability of amodiaquine is decreased due to first-pass hepatic metabolism. The plasma protein binding rate of amodiaguine and desethylamodiaguine is greater than 90%. The T_{max} of amodiaguine taken orally by patients with falciparum malaria is 1.75h, distinctly longer than the T_{max} of healthy volunteers (18).

Potential interactions through hepatic metabolism

All study drugs are metabolized in the liver. Artemether and lumefantrine are primarily metabolized via CYP3A4 (19). Artemether metabolism through CYP3A4 produces an active metabolite, dihydroartemisinin (DHA) that contributes substantially to its antimalarial activity. Artemether is also a CYP3A4 inducer, while lumefantrine inhibits CYP2D6 (20). The clearance of amodiaquine and metabolism to its main metabolite, N-desethylamodiaquine, is catalyzed primarily by CYP2C8 (21). As some of these drugs share the same enzymes or have effects on the enzymes for other drug metabolism, the co-administration may result in clinically significant drug-drug interactions that can cause unanticipated adverse reactions or therapeutic failures. To evaluate whether such effects take place, we propose to co-administer these drugs in this healthy volunteer study.

2. OBJECTIVE(S)

2.1. Primary Objective

• To characterize the potential pharmacokinetic interactions of artemether - lumefantrine and amodiaquine in healthy adult subjects.

2.2. Secondary Objectives

- To characterize the pharmacokinetic properties of artemether-lumefantrine and amodiaquine when given alone and in combination.
- To evaluate the safety and tolerability of co-administered artemether-lumefantrine and amodiaquine.

• To investigate pharmacogenetic polymorphisms affecting drug levels of artemetherlumefantrine and amodiaquine and their metabolites.

2.3. Exploratory Objective

• To evaluate independent renal markers against standard blood urea nitrogen/ creatinine levels as markers of renal toxicity.

3. ENDPOINT(S)

3.1. Primary Endpoint

• Area under the concentration-time curve (AUC0-∞ and AUC0-last) and maximum concentration (Cmax) of artemether, lumefantrine and amodiaquine and their metabolites when given alone and in combination.

3.2. Secondary Endpoints

- Elimination clearance (CL/F), terminal elimination half-life (t1/2) and apparent volume of distribution (Vd) of artemether, lumefantrine and amodiaquine and their metabolites when given alone and in combination.
- Safety and tolerability parameters, including adverse events, electrocardiographic changes, vital signs and biochemical assessments.
- Pharmacogenetic polymorphisms in the case of unusual metabolizer.

3.3. Exploratory Endpoint

• Independent renal marker blood levels and standard blood urea nitrogen/creatinine levels.

4. STUDY DESIGN

This is an open-label pharmacokinetic study in 16 healthy Thai subjects. Subjects will be admitted in the inpatient ward and will be randomized to **group A** or **group B** to receive 3 drug regimens described in the following table 1. Every subject will have 1 screening and 3 admissions in the hospital.

Visit 1	Screening					
	Within 14 days					
	Group A (n = 8)	Group B (n = 8)				
Visit 2	Regimen 1	Regimen 2				
	Artemether-lumefantrine	Amodiaquine				
	on Day 0, 1, and 2	on Day 0, 1 and 2				
	Washout period: > 6 we	eeks (after day 3)				
Visit 3	Regimen 2	Regimen 1				
	Amodiaquine	Artemether-lumefantrine				

 Table 1: Study Schedule

	on Day 0, 1 and 2	on Day 0, 1 and 2		
Washout period: > 6 weeks (after day 3)				
Visit 4	Regimen 3			
	Artemether-lumefantrine + Amodiaquine on Day 0, 1 and 2			

The total duration for each subject's participation in the study is approximately 6 - 8 months depend on washout period. Study duration is approximately 12 months.

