2.2 PRIMARY ENDPOINT

Area under the concentration-time curve (AUC_{0-∞} and AUC_{0-last}) and maximum concentration (C_{max}) of artemether, lumefantrine and amodiaquine and their metabolites when given alone and in combination.

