2.5 GENERAL

This is an open-label pharmacokinetic study in 16 healthy Thai subjects. Subjects will be admitted in the inpatient ward and will be randomized to Artemether-lumefantrine followed by Amodiaquine or Amodiaquine followed Artemether-lumefantrine. There will be a washout period: > 6 weeks (after day 3) and then each of the participants will be given Artemether-lumefantrine + Amodiaquine. Thus, eEvery subject will have 1 screening and 3 admissions in the hospital.

All subjects will undergo screening assessments (visit 1). Screening assessments (visit 1) may be carried out over more than one day, provided that all required assessments are completed within the 14 days prior to visit 2. If the interval between screening (visit 1) and day -1 visit 2 is three days or less, the clinical laboratory screening test result and serum pregnancy test result can be used for enrolment evaluation on day -1 visit 2. In such cases, these tests would not need to be repeated at day1 visit 2

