3.5.2 Pharmacokinetic assessments

Individual pharmacokinetic parameters of artemether/dihydroartemisinin, lumefantrine/desbutyl-lumefantrine and amodiaquine/desethylamodiaquine will be calculated after each dose administration using a non-compartment approach.

Total exposure up to the last measured concentration (AUC_{LAST}) will be calculated using the linear trapezoidal method for ascending concentrations and the logarithmic trapezoidal method for descending concentrations. The terminal elimination half-life ($t_{1/2}$) will be estimated by the slope (λ_Z) of the best-fit log-linear regression of the observed concentrations in the terminal elimination phase. Drug exposure will be extrapolated from the last observed concentration to time infinity by C_{LAST}/λ_Z for each individual subject to compute total drug exposure (AUC_{∞}). Maximum concentration (C_{MAX}) and time to maximum concentration (T_{MAX}) will be taken directly from the observed data. Apparent oral elimination clearance (CL/F) and apparent volume of distribution (V/F) will be computed individually according to the equations below.

$$CL/F = \frac{Dose}{AUC_{\infty}} \quad V/F = \frac{t_{1/2} \times CL/F}{\ln 2}$$

The pharmacokinetic parameters will be summarised for each drug stratified by arm (i.e., when administered alone or in combination). Similarly, descriptive statistics will be summarised by arm. Ln-transformed pharmacokinetic exposure parameters (C_{MAX} , AUC_{LAST} and AUC_{∞}) will be evaluated to assess potential drug-drug interactions. No drug-drug interaction is assumed if the 90% confidence intervals of the ratio (combination/alone) of C_{MAX} , AUC_{LAST} and AUC_{∞} fall within 80% to 125% [10]. The 90% confidence intervals of the ratio (combination (COMB)/alone (ALONE)) will be calculated according to equation below.

$$Mean\ ratio\ (\%) = 100 \cdot e^{Parameter_{combination} - Parameter_{alone}}$$

where $Parameter_{combination}$ and $Parameter_{alone}$ are the least square mean of the natural logarithm of parameters derived for the combination and alone administration, respectively. The upper and lower boundary of the 90% confidence interval are calculated as follow:

$$90\% \ Confidence\ Interval = 100 \cdot e^{(Parameter_{combination} - Parameter_{alone}) \pm t_{0.95} \cdot SE_D}$$

STATISTICAL ANALYSIS PLAN FOR ALAQ STUDY

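### Desethylamodiaquine left over from the amodiaquine-alone regimen can inflate the combination/alone ratios, and the SAP has no correction for it

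*Protocol*

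**What the plan says.** Protocol section 4 randomises 16 subjects to two sequences of 8. Group A takes artemether-lumefantrine (AL), then amodiaquine (AQ), then both. Group B takes AQ, then AL, then both. Table 1 separates the regimens by "Washout period: > 6 weeks (after day 3"), with no upper limit. Participation is given as "approximately 6 - 8 months depend on washout period". SAP 2.5 repeats the order: after the washout "and then each of the participants will be given Artemether-lumefantrine" plus amodiaquine.

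The introduction gives an elimination half-life "of desethylamodiaquine in plasma is 9-31 days". It describes lumefantrine "with an elimination half-life of 3 to 6 days in healthy volunteers". It gives no half-life for desbutyl-lumefantrine.

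The primary endpoint (SAP 2.2) is AUC0-∞, AUC0-last and Cmax of "artemether, lumefantrine and amodiaquine and their metabolites when given alone and in combination", and SAP Table 3 has a DEAQ column. Under SAP 3.5.2, Cmax "will be taken directly from the observed data" and AUC is integrated from the measured concentrations. The decision rule there reads: "No drug-drug interaction is assumed if the 90% confidence intervals of the ratio (combination/alone") lie within 80–125%. Protocol 12.5.1 uses the same non-compartmental approach. Neither document subtracts a pre-dose level, excludes profiles that have one, or assesses carry-over. Yet protocol Table 2 includes an hour-0 pre-dose sample in every regimen, and actual sampling times are recorded.

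**The concern.** AQ alone is never preceded by AQ, whereas the combination always is: one washout earlier in Group A and two in Group B. Residual DEAQ therefore adds to the combination profile and never to the alone profile. Randomising the first two regimens cannot balance this, and the two groups are affected unequally.

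The ratio is pushed upward. It may suggest an interaction that does not exist. More seriously, it may lift a truly reduced DEAQ exposure off the 80% limit and produce a false finding of no interaction. The introduction names suboptimal exposure and treatment failure as reasons for studying interactions, so that is the error the trial most needs to avoid.

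**Working it through.** The documents give no carry-over figure, so there is none to reproduce.

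**1. Washout implied by the protocol.** With washout W counted from day 3, participation = 14 (screening) + 1 + 2(W + 3) + 42 (follow-up) days.
- W = 60: 14 + 1 + 126 + 42 = 183 days, 6.0 months.
- W = 90: 14 + 1 + 186 + 42 = 243 days, 8.0 months.
- W = 42 (the floor): 14 + 1 + 90 + 42 = 147 days, 4.8 months, shorter than stated.

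So 60 to 90 days is the working range and 42 days is the permitted extreme. At the floor, Day 0 to Day 0 is 45 days: 45/9 = 5.0 half-lives, or 45/31 = 1.5.

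**2. Simple bound, single-exponential decline.** Residual AUC as a share of the regimen's own AUC0-∞ is r = 2^(−T/t½), with T = W + 3 days in Group A and 2(W + 3) in Group B. With no true interaction, pooled ratio = √[(1 + rA)(1 + rB)].

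| t½ (all subjects) | W | rA | rB | Pooled AUC ratio |
|---|---|---|---|---|
| 9 d | 60 | 0.8% | 0.0% | 1.004 |
| 20 d | 60 | 11.3% | 1.3% | 1.061 |
| 20 d | 90 | 4.0% | 0.2% | 1.020 |
| 31 d | 60 | 24.5% | 6.0% | 1.148 |
| 31 d | 90 | 12.5% | 1.6% | 1.069 |

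For example, at 20 d and W = 60: √(1.1127 × 1.0127) = 1.061.

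**3. Fuller profile.** A single-dose DEAQ curve (first-order formation, bi-exponential decline) was fitted to the introduction's plasma values: Cmax 181 ng/mL at 3.4 h, AUC0-24 2304 ng·h/mL, and 29 at 96 h (unit garbled; taken as ng/mL). The six doses at 0, 8, 24, 36, 48 and 60 h were superposed. Parameters were computed at the Table 2 times (linear up, log down). Half-lives were spread uniformly over 9–31 d, an assumption because only the range is given.

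| W | AUC0-∞ A / B / pooled | Cmax A / B / pooled |
|---|---|---|
| 42 d | +19.6 / +5.0 / +12.1% | +10.1 / +2.6 / +6.3% |
| 60 d | +11.1 / +1.8 / +6.4% | +5.7 / +0.9 / +3.3% |
| 90 d | +4.6 / +0.4 / +2.5% | +2.3 / +0.2 / +1.3% |

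AUC0-last is within 0.2 points of AUC0-∞. A log-uniform spread gives a pooled AUC of +4.9% at 60 d and +1.8% at 90 d (Cmax +2.6% and +0.9%). At a 20 d half-life and 60 d washout, moving the 96 h input from 14.5 to 37 changes the AUC0-∞ ratio only from 1.055 to 1.061, and Cmax from 1.019 to 1.037.

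**4. Effect on the decision.** No CV is stated, so within-subject CVs of 15, 20, 25 and 30% are assumed. For a paired two one-sided test, SE = √[ln(1 + CV²)] × √(2/16), with t0.95 = 1.753 on 15 df.

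| Condition | CV 15 / 20 / 25 / 30% |
|---|---|
| False no-interaction, true ratio 0.80, no bias | 5 / 5 / 5 / 4% |
| Same, bias 1.02 | 10 / 9 / 8 / 6% |
| Same, bias 1.06 | 28 / 20 / 15 / 11% |
| Meeting 80–125%, true ratio 1.00, no bias | 98 / 84 / 58 / 33% |
| Same, bias 1.06 | 91 / 71 / 49 / 29% |

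Simulating whole trials (4,000 of 16 subjects, half-lives over 9–31 d, 10% concentration error, W = 60, true ratio 0.80) gives 34, 27, 21 and 16% for AUC0-∞ and 19, 14, 12 and 10% for Cmax. These exceed the fixed 1.06 case because the residual comes from the unreduced alone regimen: it adds about 0.06 to 0.80, a relative bias of about 0.86/0.80 = 1.08. At W = 90 the AUC0-∞ rates are 12, 11, 9 and 7%.

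**5. Other analytes.** Parent amodiaquine (5.2 h) is negligible. Lumefantrine leaves at most 0.6% in Group B at W = 42 (6 d half-life, averaged over the six doses). For desbutyl-lumefantrine, assumed half-lives of 3, 6, 9 or 12 d give a Group B residual of 0, 0.6, 3.4 or 8.0% at W = 42 and 0, 0.1, 0.9 or 2.8% at W = 60. The pooled effect is about half.

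**The case against.** The size rests on assumptions. The protocol gives a bare half-life range, and a common half-life anywhere within it moves the 60-day AUC bias between 0.4% and about 15%. The washouts of 60 to 90 days are inferred. At 90 days the damage is small: with a bias of 1.02, the chance of meeting 80–125% at a true ratio of 1.00 is 98, 82, 57 and 32%, against 98, 84, 58 and 33% without bias. The largest error rates combine the shorter implied washout, the worst parameter and a true ratio exactly on the limit. They also come from a paired analysis, whereas the plan specifies ANOVA with least-squares means. All of this stands as a limit on the numbers. None of it removes the omission or changes the direction of the bias, and the shift would persist under ANOVA.

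The correction is also imperfect. It relies on one pre-dose value and a slope from three late samples, and it was tested largely under the model it assumes. If Group B hour-0 levels fall below an assay limit the documents do not give, it would work only in Group A. Those costs are real and are set out with the fix. The desbutyl-lumefantrine figures rest wholly on assumed half-lives, so they show only that carry-over cannot be excluded for that metabolite.

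**Conclusion.** The concern holds. Followed as written, the plan biases the DEAQ combination/alone ratios upward for all three primary parameters. The omission and the direction follow directly from the documents.

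The size is conditional. With half-lives spread over 9–31 days and linear kinetics, the pooled bias is about 2–6% for AUC and 1–3% for Cmax at washouts of 90 to 60 days, nearly all of it from Group A. At the 42-day floor it reaches about 12% and 6%, though that schedule is shorter than the stated participation. The bias alone does not breach 80–125%. At the shorter implied washout, however, it can raise the risk of missing a 20% fall in DEAQ AUC0-∞ from about 5% to between 16 and 34%, depending on the CV. This should be fixed before the data are analysed.

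**What to change.** In SAP 3.5.2, pre-specify the following for any analyte quantifiable in a regimen's hour-0 sample (expected for DEAQ at Visit 4).

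- Subtract C0·exp(−λz·t), at actual sampling times, from each post-dose concentration before deriving Cmax, AUC0-last and AUC0-∞. Set C0 to 0 if not quantifiable, and negative results to 0.
- Use the subject's own Visit 4 λz for the primary correction and the AUC0-∞ tail. Use the alone-regimen λz as a sensitivity analysis.
- Base the 80–125% decision on the corrected ratio. Report corrected and uncorrected ratios, overall and by sequence group.

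The Visit 4 slope is preferred because co-administration may itself alter elimination. If it speeds DEAQ elimination by 20% (20 d half-life, W = 60), the true AUC0-∞ ratio is 0.844. The uncorrected analysis gives 0.894, the Visit 4 slope 0.844 and the alone slope 0.835.

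The cost is SAP text and a few lines of code on samples already planned. In the simulation at W = 60 the false no-interaction rate returns to 4–6% for all three parameters. The chance of meeting 80–125% for AUC0-∞ at a true ratio of 1.00 moves from 82, 63, 46 and 29% to 95, 76, 52 and 28% (CV 15–30%).

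There are three downsides. At a 31 d half-life and W = 60, the Group A SD of the log ratio rises from 0.060 to 0.079 for AUC0-last and from 0.092 to 0.098 for Cmax. At CV 30% up to 3 points of power are lost. If Group B hour-0 levels are not quantifiable, 0.6% AUC and 0.3% Cmax bias remain at 20 d (2.9% and 1.5% at 31 d). The washout and participation text need not change.
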